Risks for this cohort include side effects from PrEP provided to the young men through the study clinic, and discomfort associated with blood draws, interviews, and STI and HIV counseling and testing. Intensive and ongoing counseling and monitoring of side effects and adverse events limit the risk for participants from the direct study procedures.

For clinical data collection, standardized surveys will be used that will include questions on sensitive topics, such as sexual behavior. All participants will be extensively counseled about the risk and prevention of STIs, as well as the risk for HIV transmission with sex unprotected by a condom and/or PrEP and the importance of using condoms consistently and correctly. We expect that the risk of HIV transmission will actually be lower in this cohort than the general population of young men due to the careful attention that will be given to counseling about HIV risk and the provision of PrEP. Study staff will be aware of the potential for confidentiality issues with regards to test results from HIV testing that are part of a participant's study documents.

There is the potential for confidentiality issues with regards to study data. Although the study site will make every effort to protect participant privacy and confidentiality, it is possible that participants' involvement in the study could become known to others, and that social harms may result. However, the research staff has extensive experience in both individual and couples counseling, particularly on the topics of serodiscordance and HIV status disclosure. The research staff will provide couples counseling if the male participant chooses to involve their study partner, or individual counseling if the male participant chooses to keep his STI/HIV results confidential.

D. Benefits

Participants will receive individualized HIV and STI risk-reduction counseling and testing, access to PrEP medication, and free condoms. In addition, participants may benefit in the future from information learned from this study.

E. Care for persons identified as HIV positive

Men who test positive for HIV at enrollment or become infected with HIV later in the study will be referred immediately to HIV care centers and encouraged to initiate antiretrovirals in line with Ugandan national antiretroviral guidelines.

F. Treatment for injury

Participants will be asked to inform the clinic staff if they feel they have been injured because of taking part in the study. Injuries may also be identified during laboratory testing, and medical histories. Treatment for adverse events related to study participation will be provided by the research clinic. If treatment is required that is beyond the capacity of the clinic, the clinic staff will refer the participant to appropriate services or organizations that can provide care for the injury. The study based at IDI will cover the costs of the referral and treatment costs up to the time the participant is stable, or injury is resolved.

F. Study records

Complete, accurate, and current study records will be maintained and stored in a secure manner throughout the study. Study records include administrative documentation and regulatory documentation as well as documentation related to each participant enrolled in the cohort, including informed consent forms, chart notes, case report forms, laboratory requisitions, notations of all contacts with the participant, and all other source documents.

G. Confidentiality

Every effort will be made to protect participant privacy and confidentiality to the extent possible. Personal identifying information will be retained at the local study site.

X. CLINICAL RESEARCH SITE

A. Site location

The Infectious Diseases Institute (IDI)-Kasangati research clinic is part of the Infectious Diseases Institute, Makerere University College of Health Sciences. The facility is located next to Kasangati Health Center IV and has adequate space and equipment for ongoing and planned research studies. The Infectious Diseases Institute training team offers specialized courses in HIV management for health providers in Africa. For this study the focus of the training will be combination HIV prevention services including PrEP as well as STI prevention and treatment.

B. Clinical facilities

The site has a large training room that can accommodate up to 50 people, 3 clinical rooms, 6 counseling rooms, a pharmacy, a phlebotomy room, a side lab, secure data room with data archive, administrative office space, wireless internet, telephone intercom system, community education offices, and a large waiting area which provide sufficient space for the execution of this study.

C. Staff

The Principal Investigator is a seasoned HIV/AIDS researcher and trainer, of local and international repute. He will lead the study team to maximize the scientific, ethical integrity of the study and ensure the training provided is of high quality. The study employs in total doctors, nurse counselors, a pharmacy technician, laboratory staff and community educators/counselors, data personnel, qualitative research associates as well as support and administrative staff. The respective staff are overseen by a site coordinator, training coordinator and administrator. The study site previously implemented the Partners PrEP Study and the Partners Demonstration Project and is currently implementing the KWBS. The staff have substantial experience in the use of PrEP and its accompanying supportive services. The staff have been involved in the conduct of protocol specific training, development of outreach materials, and have skills in training of adult learners.

D. Administrative procedures

All administrative procedures regarding protocol compliance, study coordination, study activation, study monitoring, study records, and use of information and publications will be done according to good clinical practice.

E. Laboratory considerations

We will as much as possible use the public health laboratory facilities for routine laboratory monitoring. In situations where this is not possible, specimens will be collected and transported to the study collaborating laboratories. All specimen collection, transport, processing, testing, archiving, and results reporting will be conducted in accordance with good clinical and laboratory practice standards. The collaborating laboratories for the research clinic are the IDI Core Laboratory and the Immunology Laboratory in the Department of Medical Microbiology at Makerere College of Health Sciences. These are well-established labs with extensive experience in supporting clinical trials. External Quality Assurance (EQA) procedures will be followed

throughout the study and are overseen by the University of Washington International Clinical Research Center.

XI. DATA SHARING AND OWNERSHIP

During the conduct of the trial, the study database will remain confidential. After study completion, access to data will follow requirements of the Infectious Diseases Institute, National Institutes of Health and the University of Washington. The University of Washington International Clinical Research Center has a Manuscripts and Ancillary Studies Committee established to enable data and specimen collaborative work from studies conducted through the research group. Intellectual property and data generated under the proposed project will be administered in accordance with Uganda, University of Washington and NIH policies, including the National Guidelines for Research involving Humans as Research Participants (2014) [113] and the NIH Data Sharing Policy and Implementation Guidance of March 5, 2003.

Materials generated under the project will be disseminated in accordance with University/participating institutional and NIH policies. Depending on such policies, materials may be transferred to others under the terms of a material transfer agreement. Access to databases generated under the project will be available for educational, research and non-profit purposes as approved by the relevant IRBs. Publication of data shall occur during the project, if appropriate, or at the end of the project, consistent with normal scientific practices. We will publish our findings in a timely fashion and will present unpublished data at appropriate research conferences. We are committed to collaboration in complex disease research and will participate in data-pooling studies as allowed by our currently established consent forms and IRBs.

Data obtained from this research study are the property of the Infectious Diseases Institute of Makerere University and the University of Washington International Clinical Research Center. Local researchers shall have unrestricted access rights to datasets collected through this collaborative research project in accordance with Uganda guidelines.

XII. DISSEMINATION PLAN

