Following informed consent, men will be screened for their willingness to comply with study procedures, complete locator information, and assigned a unique ID. Eligible men will be enrolled into the study, on the same day if possible. Procedures on the day of enrollment will include: 1) HIV testing with PrEP dispensation or active referral to ART and HIV care depending on the results, 3) Hepatitis B and creatinine testing for men starting PrEP, 2) completion of questionnaires to assess demographic information, recent sexual behavior, partnership status, HIV risk perception, alcohol and drug use, mental health, and adherence to ART/PrEP, 4) diagnostic testing for *N. gonorrhoeae* and *C. trachomatis* using rapid tests with real time results. Results from creatinine testing will be available within 3-5 days from the laboratory. Any participants with abnormal creatinine/creatinine clearance will be contacted by the study clinician and asked to return for confirmatory testing. PrEP will be discontinued for any men with confirmed abnormal creatinine/creatinine clearance levels according to national guidelines.

Follow up

Follow up visits will be conducted 1, 3 and 6 months after enrollment. Procedures at each visit will include: 1) HIV testing with PrEP dispensation or referral to ART and HIV care depending on the results, 2) completion of questionnaires to assess recent sexual behavior, partnership status, HIV risk perception, and adherence to ART/PrEP, and 3) diagnostic testing and treatment for *N. gonorrhoeae* and *C. trachomatis*.

Aligning PrEP and HIV Study Protocol

Version 1.0

23rd July 2019

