gonorrhoeae and *C. trachomatis*. PrEP use will be objectively measured by point-of-care urine tests, if kits become available during the study, and real time monitoring of PrEP adherence will be conducted using an electronic monitoring system that captures a date-time stamp each time the pill container is opened, if devices become available.[27] Participants using PrEP will have a creatinine test at the 6-month/study exit visit which aligns with Uganda national PrEP guidelines. For men who test HIV-positive, confirmatory HIV testing will be conducted according to Uganda national guidelines and PrEP will be discontinued. HIV-positive men will continue to be engaged until the end of their follow up time to collect sexual behavior data, but HIV testing will not be conducted once HIV-positive status is confirmed. Men will be counseled about ART initiation and ART adherence and HIV viral load testing will be conducted when HIV is first detected and 3 months after ART initiation. IDIK is situated next to a public health facility that provides ART and is often a close collaborator to receive referred research participants for HIV care.

Visit-specific procedural tables

	SCR	ENR	M1	M3	M6 & EXIT
ADMINISTRATIVE & REGULATORY PROCEDURES					
Obtain informed consent	X	X			
Collect/update locator information	X	X	X	X	X
Collect/update demographic information	X	X			
CLINICAL & COUNSELING PROCEDURES					
HIV pre and post-test counseling	X	X	X	X	X
Risk reduction counseling & condom provision	X	X	X	X	X
If HIV negative: PrEP counseling, including adherence counseling	X	X	X	X	X
If HIV negative: PrEP provision, if desired	X	X	X	X	X
If HIV negative: PrEP pill count, if using PrEP			X	X	X
If HIV negative: Urine TFV testing (when kits are available), download of electronic monitoring data (if devices are available)			X	X	X
If HIV positive: ART referral	X	X	X	X	X
If HIV positive: ART counseling	X	X	X	X	X
Diagnostic testing and/or syndromic management of STIs	X	X	X	X	X
STI treatment	[X]	[X]	[X]	[X]	[X]
LABORATORY PROCEDURES					
If HIV negative: Creatinine testing when using PrEP	X				X
If HIV negative: HBV surface antigen	X				
HIV rapid test	X	X	X	X	X

If rapid test positive: Confirmatory HIV testing and RNA quantification	[X]	[X]	[X]	[X]	[X]
BEHAVIORAL DATA COLLECTION					
Questionnaire completion		X	X	X	X
Medical History questionnaire	X	X	X	X	X
X required procedure; [X] if clinically indicated					

Study exit

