Kidney function will be monitored at PrEP initiation and 6 months later, in accordance with Ugandan guidelines, using creatinine clearance calculated by Cockroft–Gault equation. The investigators will be responsible for continuous close monitoring of all adverse events that occur among study participants. For the purposes of this study, only serious adverse events (SAEs) and adverse events felt related to PrEP will be documented on case report forms. Adverse events and the severity of clinical symptoms will be scored using the DAIDS Table for Grading the Severity of Adult and Pediatric AEs.[28] The study safety monitor will review clinical and laboratory SAEs in real time as they are reported by the site clinicians on CRFs and through email within 48 hours of occurrence. As needed, the safety monitor will work to provide rapid consultation with clinicians regarding the management of toxicities. A Safety Review Team comprised of the study investigators and lead clinicians will review clinical and laboratory safety reports summarizing SAEs via conference call on an approximately quarterly basis.

VI. DATA COLLECTION

Demographic, behavioral and clinical data including STIs symptoms, sexual activity and PrEP adherence will be recorded electronically on case report forms (CRFs) directly entered by research staff into a secure web-based data management program. Results from off-site laboratory testing will be returned to the IDI research clinic and also entered into this system. Automated legal range checks will be programmed to reduce data entry errors and internal quality control reports will be run on a monthly basis. Paper backup forms will be available in the case of power or internet outages with online data entry once restored. On a weekly basis, the University of Washington data manager will archive a backup copy of the master dataset on secure servers at the University of Washington.

VII. LINKAGE WITH DATA FROM WOMEN IN THE EXISTING KWBS COHORT

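### The creatinine schedule in the procedures table does not match the text for men who start PrEP at month 1 or 3, and for them the later kidney test promised in Section V.P falls after study exit

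*Combined protocol and SAP*

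**What the plan says.** Creatinine timing is given in four places.

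- Section V.N, Procedures for men, Screening and Enrollment: among the procedures for the day of enrolment is "Hepatitis B and creatinine testing for men starting PrEP". The same paragraph says of screening and enrolment: "Eligible men will be enrolled into the study, on the same day if possible".
- Section V.N, Follow up: the procedures for each of the month 1, 3 and 6 visits include "HIV testing with PrEP dispensation or referral to ART and HIV care depending on the results", but not creatinine. A later sentence adds one fixed test: "Participants using PrEP will have a creatinine test at the 6-month/study exit visit which aligns with Uganda national PrEP guidelines".
- Section V.N, Visit-specific procedural tables: the row "If HIV negative: Creatinine testing when using PrEP" is marked at screening (SCR) and at M6 & EXIT, and is blank at ENR, M1 and M3. The row "If HIV negative: PrEP provision, if desired" is marked in all five columns. The key reads "X required procedure; [X] if clinically indicated", and the creatinine row carries no bracketed mark.
- Section V.P, Safety monitoring: "Kidney function will be monitored at PrEP initiation and 6 months later, in accordance with Ugandan guidelines".

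Under Study exit in Section V.N, the last visit is about 6 months after enrolment, with referral to a clinic of the man's choice.

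**The concern.** Section V.P counts both tests from the man's own PrEP start. The table and the follow-up text count from study visits. The two clocks agree only if PrEP starts at enrolment, yet the plan allows a start at any visit, and Aim 3 tracks PrEP initiation as part of the study. The background section reports that some women in the parent study (KWBS) who at first declined PrEP took it up later, so late starts are foreseeable.

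A safety check is at stake, not the estimation of the aims. The enrolment text sets out what happens after an abnormal result: recall, confirmatory testing and, if confirmed, discontinuation. That sequence begins only when a result exists. Staff who follow the visit table alone would have no scheduled test for a man starting at month 1 or 3, and the second test in Section V.P could not be done within follow-up.

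**Working it through.** The plan gives no figure to reproduce. The check sets the two table rows side by side and then counts months from each possible start.

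**Table rows (Section V.N)**

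| Visit | PrEP provision | Creatinine |
|---|---|---|
| SCR | X | X |
| ENR | X | blank |
| M1 | X | blank |
| M3 | X | blank |
| M6 & EXIT | X | X |

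Of five visits at which PrEP may be provided, two carry a creatinine mark and three do not.

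**Timing by start visit, in months from enrolment**

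Inputs: start month s; fixed later test and exit at about month 6 (Section V.N, Follow up and Study exit); second test at s + 6 (Section V.P). The interval from start to the fixed test is 6 − s.

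| Start | Test scheduled at the start visit? | Interval to the month 6 test | Second test under V.P | Within follow-up? |
|---|---|---|---|---|
| Screening, enrolment and start on one day (s = 0) | Yes: table, enrolment text and V.P agree | 6 − 0 = 6 months | 0 + 6 = month 6 | Yes |
| Enrolment on a separate day (s = 0) | Enrolment text yes; table marks SCR only | 6 − 0 = 6 months | 0 + 6 = month 6 | Yes |
| Month 1 | No, in table or follow-up list | 6 − 1 = 5 months | 1 + 6 = month 7 | No |
| Month 3 | No, in table or follow-up list | 6 − 3 = 3 months | 3 + 6 = month 9 | No |
| Month 6 | Yes, table | Same visit | 6 + 6 = month 12 | No |

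For month 1 and month 3 starters, the sentence fixing the later test at exit and the sentence in V.P give different times (month 6 against month 7 or 9), and both cite Ugandan guidelines. The documents do not reproduce those guidelines, so this review cannot say which timing they support.

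**How many men**

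The documents give no number of late starters among the planned 200 men. Table 3 describes women in KWBS: 91% started PrEP at enrolment, so 100 − 91 = 9% did not, and PrEP was dispensed for 17% of the person-time of those who did not. Carried over to men purely as an assumption, 9% of 200 is 18 men who might start late. That would be the ceiling if every one of them later started. The 17% is a share of person-time, not of persons, so it does not say how many of the 18 would start. On this assumption the range is 0 to 18, and the true number is unknown.

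**The case against.** The strongest reply is that the requirement already exists. Section V.P calls for a test at PrEP initiation without limiting it to enrolment, and a blank cell in the table does not forbid a test. A clinician who tests a man at a month 1 or month 3 start satisfies V.P and breaches nothing in V.N. On the path the plan prefers, with screening, enrolment and start on one day, all the statements agree. The study runs at one clinic whose staff, according to Section X.C, know PrEP well, and men leaving the study are referred for further care.

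Much of this stands, and it rules out several stronger readings that a reader might infer:

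- That the sections cannot all be followed. For the first test they can, by testing beyond what the table requires. Only the second test for later starters cannot be done within follow-up.
- That every man starting after screening lacks a test when he starts. A month 6 starter has a mark at that visit, and the text covers a start on the day of enrolment.
- That a test at initiation is missing from the plan. V.P states it; the table and the follow-up list do not carry it.
- That a screening mark contradicts a row for men using PrEP. The table also marks PrEP provision at screening.
- That Table 3 yields a firm count of affected men. It concerns women in another study, and its relevant figure is person-time.

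The reply does not remove the mismatch. The key separates required from clinically indicated procedures, and creatinine has neither mark at M1 or M3. Reading the screening mark as a test of every HIV-negative man would give late starters an earlier baseline, but not a test at initiation, and the row label does not clearly support that reading. Referral at exit does not say who obtains a test due at month 7 or 9.

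**Conclusion.** The point holds as an internal inconsistency of limited scope. For men who start PrEP at month 1 or 3, the table and the follow-up list schedule no creatinine test at initiation although Section V.P promises one, and the second test in V.P falls about 1 or 3 months after exit (7 − 6 and 9 − 6). A lesser mismatch arises when enrolment is on a separate day from screening: the table places the first test at screening, the text on the day of enrolment. For a same-day start there is no conflict.

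The conclusion assumes that V.P counts six months from each man's own start, as its wording indicates, and that exit is about six months after enrolment. The number of men affected is not given. The aims, outcomes and analysis are not touched, but a stated safety check is, and the correction is cheap enough that it should be made.

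**What to change.** Reconcile three parts of Section V.N (the enrolment text, the follow-up text and the visit table) with Section V.P so that all give the same creatinine schedule. The reconciled text should state explicitly what applies to:

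- men who first take PrEP at month 1 or month 3;
- men whose second test would fall after exit, including who is responsible for it if it is kept;
- men enrolled on a different day from screening.

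Whether tests are counted from PrEP start or from study visits is for the sponsor's clinicians to decide; this review does not favour either. The cost is a correction to one table row and a few sentences, and possibly a few added or moved tests.
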